8.3.2 Method of Detecting AEs and SAEs

Care will be taken not to introduce bias when detecting AEs and/or SAEs. Open-ended and non-leading verbal questioning of the subject is the preferred method to inquire about AE occurrences.

8.3.3 Follow-up of AEs and SAEs

After the initial AE/SAE report, the investigator is required to proactively follow each subject at subsequent visits/contacts. All SAEs will be followed until resolution, stabilisation, the event is otherwise explained, or the subject is lost to follow-up (as defined in Section 7.3). Further information on follow-up procedures is given in [Appendix 4](#).

8.3.4 Regulatory Reporting Requirements for SAEs

- Prompt notification by the Investigator to the Sponsor of an SAE is essential so that legal obligations and ethical responsibilities towards the safety of subjects and the safety of a study treatment under clinical investigation are met.
- The Sponsor has a legal responsibility to notify both the local regulatory authority and other regulatory agencies about the safety of a study treatment under clinical investigation. The Sponsor will comply with country-specific regulatory requirements relating to safety reporting to the regulatory authority, Independent Ethics Committees (IECs), and investigators.
- Investigator safety reports must be prepared for suspected unexpected serious adverse reactions (SUSAR) according to local regulatory requirements and Sponsor policy and forwarded to investigators as necessary.
- An investigator who receives an investigator safety report describing an SAE or other specific safety information (eg, summary or listing of SAEs) from the Sponsor will review and then file it along with the Investigator's Brochure and will notify the IEC, if appropriate according to local requirements.

8.3.5 Pregnancy

- Details of all pregnancies in female subjects and, if indicated, female partners of male subjects will be collected after the start of study treatment and until 120 days after the last dose.
- If a pregnancy is reported, the investigator should inform the Sponsor within 24 hours of learning of the pregnancy and should follow the procedures outlined in [Appendix 7](#).
- Abnormal pregnancy outcomes (eg, spontaneous abortion, fetal death, stillbirth, congenital anomalies, ectopic pregnancy) are considered SAEs.

8.3.6 Events of Clinical Interest

Selected non-serious and serious adverse events are also known as Events of Clinical Interest (ECI) and must be reported to the Sponsor.

Events of clinical interest for this trial include:

- An overdose of BO-112 and/or pembrolizumab, as defined in Section 8.4, that is not associated with clinical symptoms or abnormal laboratory results.
- An elevated AST or ALT lab value that is greater than or equal to 3x the upper limit of normal and an elevated total bilirubin lab value that is greater than or equal to 2x the upper limit of normal and, at the same time, an alkaline phosphatase lab value that is less than 2x the upper limit of normal, as determined by way of protocol-specified laboratory testing or unscheduled laboratory testing.*

*Note: These criteria are based upon available regulatory guidance documents. The purpose of the criteria is to specify a threshold of abnormal hepatic tests that may require an additional evaluation for an underlying etiology. The trial site guidance for assessment and follow up of these criteria can be made available. It may also be appropriate to conduct additional evaluation for an underlying etiology in the setting of abnormalities of liver blood tests including AST, ALT, bilirubin, and alkaline phosphatase that do not meet the criteria noted above. In these cases, the decision to proceed with additional evaluation will be made through consultation between the study investigators and the Sponsor. However, abnormalities of liver blood tests that do not meet the criteria noted above are not ECIs for this trial.

8.3.7 Disease-related Events and/or Disease-related Outcomes Not Qualifying as SAEs

The following disease-related events (DREs) are common in subjects with colorectal and GC/GEJ cancer and can be serious/life-threatening:

- Signs and symptoms unambiguously associated with disease progression.
- Death due to disease progression.

Because these events are associated with the disease under study, they will not be reported according to the standard process for expedited reporting of SAEs even though the event may meet the definition of a SAE. These events will be recorded on the corresponding AE page of the subject's eCRF within 14 days.

NOTE: However, if either of the following conditions applies, then the event must be recorded and reported as an SAE (instead of a DRE):

- *The event is, in the investigator's opinion, of greater intensity, frequency, or duration than expected for the individual subject.*
OR
- *The investigator considers that there is a reasonable possibility that the event was related to study treatment.*

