9.0 STATISTICAL CONSIDERATIONS

9.1 Statistical Hypotheses and Sample Size Determination

Approximately 80 subjects will be screened to achieve a total of 69 evaluable subjects. For both Cohort A (CRC) and Cohort B (GC/GEJ), subjects must have MSS (pMMR) disease to be considered evaluable for efficacy. This will be determined during the study and therefore subjects with MSI (dMMR) disease will be replaced. Given the low incidence of dMMR in stage IV CRC and in GC/GEJ, it is expected that this number will be low, ie, approximately 1 to 2 subjects to be replaced per cohort. Subjects with dMMR disease will be included in the safety analysis set.

The sample sizes of the cohorts were determined using Simon's 2-stage design ³⁹ to enable a first evaluation of the treatment's activity on tumour response. The designs are based on a one-sided $\alpha = 0.05$; a power 80% and response probabilities based on RECIST 1.1 noted below.

When the prespecified number of subjects for Stage 1 have been enroled and have reached the first on-study response assessment, an interim review of available data will be done by a DMC per cohort. The DMC will take the number of responses defined by the Simon's 2-stage design into consideration together with the ORR, DCR, number of subjects with Grade 3 to 5 AEs, SAEs, and individual subject tumour burden profiles to make a reasoned recommendation to the Sponsor regarding extension of each cohort to the foreseen total number of subjects. The stopping rules for futility based on the observed number of responses are considered nonbinding, leaving the final recommendation for stopping the study after Stage 1 at the discretion of the DMC members.

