9.3.2 Safety Analyses

All safety analyses will be performed on the safety analysis set separately for each cohort. In Cohort A, subjects who are dMMR will be evaluated together with pMMR subjects.

Treatment-emergent adverse events are defined as AEs that first occurred or worsened in severity after the first administration of study treatment and prior to 30 days after the last administration of study treatment.

Adverse events will be coded using the Medical Dictionary for Regulatory Activities (MedDRA). Numbers of TEAEs and incidence rates will be tabulated by preferred term and system organ class.

Treatment-emergent AEs of any grade, TEAEs with severity \geq Grade 3 (NCI-CTCAE v 5.0), TEAEs (any grade) by relationship to study treatment, TEAEs related (probable, possible or unknown causality) to study treatment with severity \geq Grade 3 (NCI-CTCAE v 5.0) SAEs, TEAEs leading to death, and TEAEs leading to discontinuation of study treatment will be tabulated for the number and proportion of subjects. Additionally, treatment tolerability will be determined by the number of study discontinuations due to treatment-related TEAEs. Commonly occurring TEAEs,

ie, those that occur in 5% or more of the subjects in either treatment group, will be summarised using descriptive statistics.

All laboratory test results, vital signs measurements, ECG results, weight, and body mass index will be summarised using descriptive statistics at each visit for raw numbers and change from baseline. The incidence of treatment-emergent abnormal laboratory, vital sign, and ECG values will also be summarised using descriptive statistics.

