
 • Any clinically significant abnormal laboratory findings or other abnormal safety assessments which are associated with the underlying disease, unless judged by the investigator to be more severe than expected for the subject's condition. • The disease/disorder being studied or expected progression, signs, or symptoms of the disease/disorder being studied, unless more severe than expected for the subject's condition. • Medical or surgical procedure (eg, endoscopy, appendectomy): the condition that leads to the procedure is the AE. • Situations in which an untoward medical occurrence did not occur (social and/or convenience admission to a hospital). • Anticipated day-to-day fluctuations of pre-existing disease(s) or condition(s) present or detected at the start of the study that do not worsen.

Definition of SAE

If an event is not an AE per definition above, then it cannot be an SAE even if serious conditions are met (eg, hospitalisation for signs/symptoms of the disease under study, death due to progression of disease).

An SAE is defined as any untoward medical occurrence that, at any dose:	
a) Results in death	
b) Is life-threatening	
The term ‘life-threatening’ in the definition of “serious” refers to an event in which the subject was at risk of death at the time of the event. It does not refer to an event, which hypothetically might have caused death, if it were more severe.

c) Requires inpatient hospitalisation or prolongation of existing hospitalisation	
In general, hospitalisation signifies that the subject has been detained (usually involving at least an overnight stay) at the hospital or emergency ward for observation and/or treatment that would not have been appropriate in the physician’s office or outpatient setting. Complications that occur during hospitalisation are AEs. If a complication prolongs hospitalisation or fulfils any other serious criteria, the event is serious. When in doubt as to whether “hospitalisation” occurred or was necessary, the AE should be considered serious.
 
Hospitalisation for elective treatment of a pre-existing condition that did not worsen from baseline is not considered an AE.

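### Section 8.3.7 puts progression events on the AE page, Appendix 4 says they are not AEs, and no section says whether they count in the all-cause safety tables or the DMC's Grade 3 to 5 count

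*Combined protocol and SAP*

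**What the plan says.** Section 8.3.7 names two kinds of disease-related event: "Signs and symptoms unambiguously associated with disease progression" and "Death due to disease progression". It exempts them from expedited SAE reporting and then states: "These events will be recorded on the corresponding AE page", with a limit of 14 days. Two exceptions send an event to SAE reporting instead: it is worse than expected for that subject, or the investigator sees a reasonable possibility that treatment caused it.

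Appendix 4, to which Section 8.3 refers for the definitions, lists among events that do not meet the AE definition: "The disease/disorder being studied or expected progression, signs, or symptoms of the disease/disorder being studied, unless more severe than expected" for the subject. Under the SAE definition it adds that an event which is not an AE cannot be an SAE, and gives death from progression as an example.

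Section 9.3.2 defines TEAEs as AEs that start or worsen between the first dose and 30 days after the last. Its list of tables includes TEAEs of any grade and of Grade 3 or higher, and ends: "TEAEs leading to death, and TEAEs leading to discontinuation of study treatment will be tabulated for the number and proportion of subjects". Section 9.1 lists among the DMC's inputs the "number of subjects with Grade 3 to 5 AEs, SAEs, and individual subject tumour burden profiles", and Section 9.4 repeats this. Neither limits the count to related events. None of these sections mentions disease-related events.

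**The concern.** The same event is placed on the AE page by one section and outside the AE definition by another, and the analysis sections do not settle how to count it. A death from progression inside the 30-day window could appear as a Grade 5, fatal TEAE at one site and be missing from the AE data of another. It could also be recorded at both sites and then counted or dropped according to how the programmer reads the plan.

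These events need not be rare. Section 8.3.7 itself describes them as common in this population. Table 6 and Appendix 6 let clinically stable subjects stay on treatment after a first radiological progression, which brings progression events inside the TEAE window. The synopsis plans about 15 centres for Stage 1 groups of 11 and 18, so small differences in site practice can move a count. There is no control arm against which the background of progression events could be judged. At stake is whether the all-cause safety figures, including those behind the Stage 1 recommendation, mean the same thing at every site.

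**Working it through.** No sample size, power or error rate is involved, so there is no planned figure to reproduce. The check is a comparison of texts, followed by an illustration of scale.

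**1. The texts side by side**

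| Question | Section 8.3.7 | Appendix 4 |
|---|---|---|
| Is the event entered on the AE page? | Yes, within 14 days | Not addressed |
| Is it an AE? | Not stated | No, unless more severe than expected |
| Can it be an SAE? | Heading says it does not qualify; text says it may meet the definition | No |
| Exception if possibly related to treatment? | Yes, reported as an SAE | None in this bullet |

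No section says which text prevails, and no eCRF marker for these events is described.

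**2. Which outputs are exposed**

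- Grade 3 or higher TEAEs and fatal TEAEs (Section 9.3.2): exposed, being all-cause.
- Any-grade TEAEs (a secondary endpoint): exposed only slightly. Section 2.2.2 reports related fever in 65% of subjects in the Phase I study, so few subjects are likely to have progression as their only TEAE.
- Grade 3 to 5 AEs shown to the DMC (Sections 9.1 and 9.4): exposed, being all-cause.
- SAE counts: less exposed, because the heading of Section 8.3.7 and Appendix 4 both keep these events out.
- Related TEAEs of Grade 3 or higher (the primary safety endpoint): largely protected, because Section 8.3.7 sends possibly related events to SAE reporting. The protection is incomplete. Section 9.3.2 counts unknown causality as related, and the Appendix 4 bullet has no relatedness exception.
- Response counts, ORR, DCR and tumour burden profiles: not exposed, so the Simon rule and its error rates are unchanged.

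**3. Scale, under an assumption**

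Let q be the share of subjects whose only Grade 3 to 5 event is progression-related. The documents give no value; 5% to 30% is assumed. If every subject were handled one way rather than the other, the expected difference in the count is n × q, and the chance that it is at least one subject is 1 − (1 − q)^n.

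| Group | n | n × q at 5% | n × q at 30% | Chance of at least 1, q = 5% | Chance of at least 1, q = 30% |
|---|---|---|---|---|---|
| Cohort A, Stage 1 | 11 | 0.6 | 3.3 | 43% | 98% |
| Cohort B, Stage 1 | 18 | 0.9 | 5.4 | 60% | 99.8% |
| Cohort A, full | 26 | 1.3 | 7.8 | 74% | more than 99% |
| Cohort B, full | 43 | 2.2 | 12.9 | 89% | more than 99% |

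For example, 11 × 0.05 = 0.55 and 1 − 0.95^11 = 0.431. Mixed practice across sites gives a difference between zero and these values. For fatal TEAEs no rate is needed to see the direction: a death from progression in the window counts if AE-page entries are counted, and does not count under Appendix 4 unless judged more severe than expected.

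**The case against.** The strongest reply is that the texts can be read together. Section 8.3 points to Appendix 4 for the definition of an AE and Section 9.3.2 builds TEAEs on AEs, so an expected progression event is not a TEAE wherever it is entered. Section 8.3.7 then says only where to write it down, as a category of its own. This reading is possible, but no section states it, and without a marker on the AE page the programmer could not apply it reliably.

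A reader might infer that a site following Appendix 4 records nothing. The appendix does not say so: it removes these events from the AE definition and gives no instruction against entering them. A reader might also infer that toxicity and progression could never be separated afterwards. That is too strong. Every AE receives a causality category, and the one for unlikely relatedness expressly covers progression. TEAEs are tabulated by relationship, individual data are listed, progression and death are captured for PFS and OS, and the DMC sees tumour burden profiles. Separation is partial, because symptoms that a site never entered may not be recoverable.

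Three further points stand. The Grade 3 to 5 count is one input to a nonbinding recommendation, with no numerical toxicity threshold. The upper part of the 5% to 30% range may be high at Stage 1, when the last subject has reached only Week 7 and entry required ECOG 0 or 1 and excluded life expectancy under 12 weeks. And Section 9.3 is a summary: the SAP it announces is not in the supplied text and could set a counting rule, though it could not restore events that sites did not record.

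**Conclusion.** The conflict is in the current text and should be resolved. It affects the all-cause tables of Grade 3 or higher and fatal TEAEs, the any-grade TEAE endpoint to a small extent, and the DMC's Grade 3 to 5 count. The size cannot be determined from the documents. The illustration, about 1 to 3 of 11 and 1 to 5 of 18 at Stage 1, rests wholly on the assumed 5% to 30% and on comparing uniform use of each reading.

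Two stronger conclusions are not supported. Fatal TEAEs might be taken for a secondary endpoint, but the synopsis lists only any-grade TEAEs, related TEAEs and discontinuations due to related TEAEs; fatal TEAEs are a planned table. The Stage 1 decision rule might be thought compromised, but its response counts do not use AE data.

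**What to change.** - Reconcile Section 8.3.7 and Appendix 4 so that every site records these events on the AE page with a mandatory disease-related-event flag. Give the Appendix 4 bullet the relatedness exception that Section 8.3.7 already has, and make the SAE wording agree.
- In Section 9.3.2, the SAP and the DMC outputs, state that the all-cause tables include flagged events. Show the Grade 3 or higher and fatal counts with and without them, and add a separate table of disease-related events.
- Do not drop flagged events from the all-cause tables. The flag is an open-label investigator judgement, and with drug injected into liver metastases, hepatic toxicity and hepatic progression may be hard to tell apart. Exclusion could hide misattributed toxicity.

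The cost is one eCRF field, a few sentences and one extra table. The change concerns recording and tabulation only.

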8.4 Treatment of Overdose

For this study, an overdose of pembrolizumab will be defined as any dose of 1000 mg or \geq 5 times the indicated dose. For BO-112 the definition of overdose is difficult since administration is via IT injections and to date there are no detectable levels of BO-112 systemically. The potential risk of overdose will likely come from leakage from the injected tumour into circulation and this may be volume related. Note there is only 1 dose/volume allowed (1 mg in 1.7 mL) in this protocol. An overdose is therefore defined for this protocol as an IT injection volume in mL which exceeds the approximate volume of the tumour and this would become applicable for injected lesions that have a diameter of < 15 mm since the corresponding volume of a sphere with this diameter is approximately 1.8 mL. In addition, any dose (inadvertently) administered outside of the intended tumoural lesion into normal liver tissue will be considered an overdose.

No specific information is available on the treatment of overdose of pembrolizumab or BO-112. In the event of overdose, the subject should be observed closely for signs of toxicity. Appropriate supportive treatment should be provided if clinically indicated.

Sponsor does not recommend specific treatment for an overdose.

In the event of an overdose, the investigator/treating physician should:

1. Contact the Medical Monitor immediately.
2. Document the quantity/description of the excess dose as well as the duration of the overdose in the eCRF.

Decisions regarding dose interruptions or modifications will be made by the investigator in consultation with the Medical Monitor based on the clinical evaluation of the subject.

8.5 Pharmacokinetics

- Plasma samples of approximately 3 mL will be collected to evaluate if BO-112 is detectable in plasma concentrations of BO-112 as specified in the SoA ([Table 1](#)). A baseline sample will be collected at Visit 1a (Cycle 1 – Day 1) at the same time as the baseline safety laboratory tests, namely before the first treatment with pembrolizumab. A unique sample will be collected during the study at Visit 1a (Cycle 1 – Day 1). This PK sample must be taken 30 to 60 minutes after the first BO-112 administration. Instructions for the collection and handling of biological samples will be provided by the Sponsor. The actual date and time (24-hour clock time) of each sample will be recorded. The time and date of study treatment administration will also be recorded.
- Samples will be used to evaluate the PK of BO-112 after first IT injection for systemic exposure. Samples collected for analyses of BO-112 plasma concentration may also be used to evaluate safety or efficacy aspects related to concerns arising during or after the study.

Any changes in the timing or addition of time points for any planned study assessments must be documented and approved by the relevant study team member and then archived in the Sponsor and study center study files but will not constitute a protocol amendment. The IEC will be informed of any safety issues that require alteration of the safety monitoring scheme or amendment of the ICF.

8.6 Pharmacodynamics

Evaluation procedure of antitumoural and immunological effects of BO-112 in the TME of the injected lesion has been described in Section 8.8.

8.7 Genetics

Not applicable to this study.

8.8 Biomarkers

- The following samples for biomarker research are required and will be collected from all subjects in this study as specified in the SoA (Table 1):
 - Tumour biopsy samples to be collected at the same intervention as the BO-112 administration at the applicable visit.
- Samples will be tested for evaluation of antitumoural effects of BO-112 in the TME of the injected lesion.

Samples may be stored for a maximum of 5 years (or according to local regulations) following the last subject's last visit for the study at a facility selected by the Sponsor to enable further analysis of biomarker responses to BO-112.

8.8.1 Immune Cell Profile of the Tumour Microenvironment

Immune cell profile of the TME in BO-112 injected and noninjected lesions will be evaluated in biopsy samples collected from all subjects according to the SoA. These samples will be tested by the Sponsor or Sponsor's designee.

The detection and characterisation of the immune cell profile of the TME in BO-112 injected and noninjected lesions will be performed using an immunohistochemistry method by or under the supervision of the Sponsor. Samples may be stored for a maximum of 5 years (or according to local regulations) following the last subject's last visit for the study at a facility selected by the Sponsor to enable further analysis of immune responses to BO-112.

